### 9.2.2 Serious adverse events (SAEs)

A serious adverse event is any untoward medical occurrence or effect that

- results in death;
- is life threatening (at the time of the event);
- requires hospitalisation or prolongation of existing inpatients' hospitalisation;
- results in persistent or significant disability or incapacity;
- is a congenital anomaly or birth defect; or
- any other important medical event that did not result in any of the outcomes listed above due to medical or surgical intervention but could have been based upon appropriate judgement by the investigator.

An elective hospital admission will not be considered as a serious adverse event.

The investigator will report all SAEs to the sponsor without undue delay after obtaining knowledge of the events, except for the following SAEs:

- SAEs that are a result of the surgical procedure
- SAEs that are unrelated to the breathing technique

The sponsor will report the SAEs through the web portal *ToetsingOnline* to the accredited METC that approved the protocol, within 7 days of first knowledge for SAEs that result in death or are life threatening followed by a period of maximum of 8 days to complete the initial preliminary report. All other SAEs will be reported within a period of maximum 15 days after the sponsor has first knowledge of the serious adverse events.

**9.2.3 Suspected unexpected serious adverse reactions (SUSARs)**

Not applicable

**9.3 Annual safety report**

Not applicable

**9.4 Follow-up of adverse events**

All AEs will be followed until they have abated, or until a stable situation has been reached. Depending on the event, follow up may require additional tests or medical procedures as indicated, and/or referral to the general physician or a medical specialist. SAEs need to be reported till end of study within the Netherlands, as defined in the protocol

**9.5 Data Safety Monitoring Board (DSMB)**

In this low risk study with no additional risks for the patient, we do not have a DSMB.

## 10. STATISTICAL ANALYSIS

### 10.1 Sample size calculation

See Section 4.4 for details.

### 10.2 Analysis sets

Analyses will be performed on an intention-to-treat (ITT) basis on all randomized patients. A per-protocol analysis set (PPS) will comprise all randomized patients excluding the non-compliant. Additional sensitivity analyses will be performed on the PPS.

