### 1.3 Aim

Slow-paced breathing in this trial is deep belly breathing around a frequency of 6 breaths per min and called Slow PACE breathing in this study. Participants will be trained in Slow PACE breathing pre-operatively and will practice the relaxation technique daily. We aim to examine the effects of Slow PACE breathing in breast cancer patients undergoing surgery on perioperative anxiety, performed at induction of anesthesia.

Performance at induction of anesthesia is chosen as defined intervention to be able to closely monitor non-compliance. If a participant does not manage to perform Slow PACE breathing after training at induction, she will be considered non-compliant.

We further aim to explore effects on blood pressure, per-operative need of hypnotics, postoperative pain and opioid use, PONV and patient satisfaction.

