### 4.4 Sample size calculation

With 75 patients per arm, 96% power would be achieved to detect a difference of 5 points in STAI-S score between intervention and control, with a mixed model analysis of repeated measures, at the two-sided 5% significance level in a design with 3 measurements per patient (baseline before surgery, at pre-operative holding and on day 1 post-operatively) having an autoregressive order 1 covariance structure when the standard deviation is 10 and the correlation between observations within the same patient is 0.6. The PASS software module for the test of two means in a repeated measures design was used for this calculation. Accounting for 5% drop-outs/non-compliant patients, 79 patients per arm (total 158) would be needed.

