**Feasibility analysis**

After inclusion of 30 patients, we plan to assess the compliance to Slow PACE breathing just before induction. A failure to compliance is when a patient in the intervention group does not perform the guided Slow PACE breathing at induction of anesthesia, defined as breathing at rate of  $\geq 10$  breaths per minute. Assuming 95% patients will comply, the lower limit of a binomial exact 95% confidence interval for the compliance rate will be 80%. If the lower limit of the 95% confidence interval for the compliance rate is below 80%, then additional strategies will be deployed to ensure patients adhere to the training of the breathing technique (e.g. weekly calls to check-up and remind the patients) and patients with failure to compliance will be reviewed for point of improvement to increase compliance.

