### *Pre-operative*

On the day of surgery, the participant will be transported to the operating room, where iv access is obtained and the participant is monitored by electrocardiogram, and pulse oximetry and non-invasive blood pressure will be measure by a cuff every 2-3 minutes (as is the normal procedure). The blood pressure at arrival on the operation will be noted (BP 0).

After the 'time-out procedure' the participant randomized in the intervention group will be asked to start with the Slow PACE breathing technique. This will be guided by the same audio-fragment provided during the training, so the participant has a recognizable breath pacer. The blood pressure (BP 1) and the respiratory rate at the start of induction will be noted in both groups.

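### Does a per-protocol set that removes intervention patients only, on a criterion observed after T1, undermine the STAI-S analysis?

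*Combined protocol and SAP*

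**What the plan says.** Section 10.2 makes intention-to-treat on all randomised patients the basis of the analyses. It then adds: "A per-protocol analysis set (PPS) will comprise all randomized patients excluding the non-compliant", and "Additional sensitivity analyses will be performed on the PPS". It does not define non-compliance there, and it does not name the outcomes to which the per-protocol set (PPS) applies.

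The definition has to be read from two other places. Section 1.3: "If a participant does not manage to perform Slow PACE breathing after training at induction, she will be considered non-compliant". The feasibility paragraph of section 4.4: "A failure to compliance is when a patient in the intervention group does not perform the guided Slow PACE breathing at induction of anesthesia", made operational as a respiratory rate of 10 or more per minute.

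On timing, section 8.3.3 (Pre-operative) says that after the time-out in the operating room "the participant randomized in the intervention group will be asked to start with the Slow PACE breathing technique", and that "the respiratory rate at the start of induction will be noted in both groups". Section 4.4 lists the three STAI-S measurements as "baseline before surgery, at pre-operative holding and on day 1 post-operatively". Section 8.3.2 places T1 shortly before surgery. Section 10.3 uses T1 and T2 as the outcomes of the primary mixed model, adjusted for baseline STAI-S and age group.

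**The concern.** Two features look wrong together.

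- **One-arm exclusion.** No control patient can meet the definition of non-compliance, so the PPS trims one arm and keeps the other whole. Randomisation no longer protects the comparison.
- **Order of events.** T1 is scored before the breathing at induction starts. Selecting on that breathing means selecting on something that follows the outcome and may depend on it: a woman who is very anxious in holding may be unable to slow her breathing soon afterwards. Removing her lowers the T1 mean of the intervention arm with no treatment effect at all.

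At T2 the order is right, but the one-arm selection remains. At stake is the value of the PPS as reassurance. A PPS result that agrees with intention-to-treat, or exceeds it, could come from selection, and the plan has no other compliance-based analysis of outcomes.

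**Working it through.** **1. The plan's own figures.** Inputs from section 4.4: 75 per arm, difference 5, SD 10, AR(1) correlation 0.6, three measurements, two-sided 5%. The variance factor of the mean of three measurements is (3 + 4 × 0.6 + 2 × 0.36)/9 = 0.68, so the SD of the mean is 10 × √0.68 = 8.25. Power is 96.0%, as stated. The allowance gives 75/0.95 = 78.9, hence 79 per arm, as stated. If the whole 5% is non-compliance, about 0.05 × 79 = 4 intervention patients leave, and the PPS is about 75 against 79.

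**2. Size of the selection bias with no true effect.** Assume a latent tendency to fail that has correlation *r* with T1 STAI-S, and that the worst fraction *q* of the intervention arm is removed. The documents give neither *r* nor any *q* other than 5%. With φ the normal density and z the normal quantile, let k = φ(z at 1−q)/(1−q):

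- q = 5%: 0.1031/0.95 = 0.109
- q = 10%: 0.1755/0.90 = 0.195
- q = 20%: 0.2800/0.80 = 0.350

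Unadjusted for baseline, the T1 shift is 10·r·k. The planned model adjusts for baseline, which removes part of it. Under AR(1) 0.6 the remaining factor at T1 is 1 − 0.6² = 0.64. At T2 it is 0.6 × 0.64 = 0.384. For the T1/T2 mean it is (0.64 + 0.384)/2 = 0.512. The bias in the mean is then 10 × 0.512 × r × k:

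| Non-compliance | r = 0 | r = 0.3 | r = 0.5 |
|---|---|---|---|
| 5% | 0 | 0.17 | 0.28 |
| 10% | 0 | 0.30 | 0.50 |
| 20% | 0 | 0.54 | 0.90 |

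Simulation with 79 per arm and baseline adjustment (20,000 runs per cell) gives 0.17 and 0.26, 0.30 and 0.52, and 0.53 and 0.89, in the same order. By visit at 5%, it gives 0.21 to 0.34 at T1 and 0.13 to 0.19 at T2. All of these favour the intervention. A negative *r* reverses the sign.

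**3. Does it change a conclusion?** The standard error of the adjusted T1/T2 mean is 10 × √(0.5696 × 2/79) = 1.20, where 0.5696 = 0.8 − 0.48² is the residual variance factor. At 5% non-compliance the bias is at most 0.28/1.20 = 0.23 standard errors, and about 5% of PPS tests fall below p = 0.05, which is nominal. The share is 5–7% at 10% non-compliance and 7–11% at 20%.

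**4. What the feasibility check does.** Section 4.4 says "If the lower limit of the 95% confidence interval for the compliance rate is below 80%, then additional strategies will be deployed". The exact lower limit is 82.8% for 29/30 and 77.9% for 28/30, so two failures among 30 intervention patients trigger it. The probability of that is 45%, 82% and 99% at true non-compliance of 5%, 10% and 20%. If only 15 of the 30 are intervention patients, even 15/15 has a limit of 78.2% and triggers it. If later patients then reach 5%, the trial-wide rate from a 20% start is (15 × 0.20 + 64 × 0.05)/79 = 7.8% to (30 × 0.20 + 49 × 0.05)/79 = 10.7%. The bias is then 0.22 to 0.54 points.

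**5. Would a replacement do better?** The natural candidate is a complier-average causal effect (CACE) with randomised arm as instrument. It assumes that patients who fail at induction gain nothing from allocation. Yet they may have had the video, the call and daily practice (sections 5.1 and 8.3.3). Each point of such gain moves the CACE by q/(1−q): 0.11 at 10% and 0.25 at 20%. Take a true complier effect of −5, a gain of half that in non-compliers, and r = 0.3, at T2:

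- 10%: CACE −5 − 2.5 × 0.11 = −5.28; PPS −5 − 0.23 = −5.23
- 20%: CACE −5 − 2.5 × 0.25 = −5.63; PPS −5 − 0.40 = −5.40

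Simulation agrees (−5.27 against −5.21, and −5.67 against −5.44). The CACE is no closer to −5, and its standard error at T2 rises from 1.48 for intention-to-treat to 1.65 and 1.87.

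**The case for a change.** The case for changing the plan is a serious one. The facts in the text are right, the bias is real if anxious patients fail more often, and that link is plausible. Where allocation truly does nothing for non-compliers, the CACE is clearly better. With a true complier effect of −5, 10% non-compliance and r = 0.5, the T1 estimates are −5.65 for the PPS, −4.51 for intention-to-treat and −5.01 for the CACE. The feasibility check does not guarantee low non-compliance, and failures before it still count. The change would cost little more than wording.

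Part of this stands. A PPS contrast in STAI-S should not be read as a randomised one, and its T1 part says nothing about breathing at induction.

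The rest carries less weight. The CACE advantage depends on an exclusion restriction that a trial with weeks of home training strains. A CACE at T1 would also need a threshold of practice days, for which the documents give no basis, applied to a self-reported yes/no log. Limiting the PPS to T2 would keep the one-arm selection, which at T2 is 0.13 to 0.67 points over the same range of assumptions. Finally, every per-protocol comparison is non-randomised, and section 10.2 claims nothing else for this one.

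**Conclusion.** The observation is correct, but no change to the plan follows. The primary inference rests on all randomised patients and is unaffected. The PPS has a sensitivity role only, and section 1.3 explains that performance at induction was chosen on purpose so that compliance could be monitored.

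The bias is nil without a link between anxiety and non-compliance. At the planned 5% it is about 0.2 to 0.3 points in the T1/T2 mean, on a 5-point target, with a nominal rejection rate. It approaches 0.9 points only with 20% non-compliance and a correlation of 0.5. These sizes rest on SD 10 and AR(1) 0.6 from section 4.4 and on assumed correlations of 0.3 to 0.5. They also assume that the PPS is applied to STAI-S, which section 10.2 does not say. The timing point does not touch MAP or propofol dose at induction.

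What remains is labelling that a competent analyst supplies when reporting: call the PPS results supportive and non-randomised, and note that compliance at induction is observed after T1. A CACE is a fair optional extra, but it trades one untestable assumption for another.

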### 10.3 Primary study parameter

For analyzing the STAI-S, a mixed model for repeated measures data (T1= pre-operative, and T2= post-operative) will be used to test for differences between study arms, adjusted for STAI-S at baseline and randomization stratification factor age group. Akaike's information criteria (corrected) and Bayesian information criteria will be used for choosing the correlation structure. Diagnostic residual plots will be used to inspect model assumptions. In a separate exploratory analysis, STAI-T at baseline (dichotomized for anxiety status with cut-off 40 (see protocol Section 8.3.2) will be added as an explanatory variable in the regression, with and without interaction with study arm. The same will be done with HADS-A at baseline, dichotomized using cut-off 8 (Section 8.3.2).

Additional analyses will be performed on the primary study parameter: Differences in STAI-S between measurements T0 and T1, between T1 and T2 and between T0 and T2 will be compared between study arms using linear regression models for each comparison, adjusting for baseline measurements.

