### 8.3.2 Measures of anxiety

#### *Baseline (T0)*

After obtaining informed consent participants will fill out the baseline questionnaires online: STAI and HADS-A.

Spielberger's State-Trait Anxiety Inventory (STAI) is a well validated and widely used method of measuring an individual's temperament or normal anxiety levels (Trait Anxiety) as well as their current or situational anxiety levels (State Anxiety). Each scale is comprised of 20 statements. The participant scores each question on a 4-point scale ranging from 1 (not at all) to 4 (very much so), with the total score ranging from 20 to 80. Higher scores indicate higher levels of anxiety symptoms. A cut-off score of 40 is commonly used to define probable clinical levels of anxiety. In this study, we will ask participants to complete both Trait and State subscales at baseline. The STAI-T will give an estimation of patients at high risk for anxiety.

Besides the STAI-T we will also take the HADS-A subscale at baseline to identify breast cancer patients with high anxiety levels. The Hospital Anxiety and Depression Scale is a questionnaire that has been found to be a reliable instrument for detecting states of anxiety and depression in a hospital setting. The HADS-A is the anxiety subscale that consists of seven items. Each item is rated on a 4-point scale (ranging from 0 = no not at all, to 3 = yes definitely), for a total score ranging from 0 to 21. A subscale score above 8 denotes anxiety.

The HADS-A is a shorter questionnaire than STAI-T and is used more commonly in the Antoni van Leeuwenhoekziekenhuis to measure general anxiety. We will compare STAI-T to HADS-A in prediction of high general anxiety.

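### Optional efficiency gain: pre-specify the continuous baseline trait score (STAI-T) as an extra covariate in the primary STAI-S model

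*Combined protocol and SAP*

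**What the plan says.** Section 10.3 defines the primary analysis as a repeated-measures mixed model for STAI-S at T1 (pre-operative) and T2 (post-operative), "adjusted for STAI-S at baseline and randomization stratification factor age group". No other baseline variable enters that model.

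Section 8.3.2 asks all participants to complete both the state and the trait scale at T0, and says of the trait scale: "The STAI-T will give an estimation of patients at high risk for anxiety". Section 8.3.3 starts training only after the baseline questionnaires, so the intervention cannot affect STAI-T.

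STAI-T is used elsewhere. Section 10.3 adds it, cut at 40, to a separate exploratory regression with and without an interaction with arm, and treats HADS-A in the same way with a cut-off of 8. Section 10.4 analyses both scores by ROC curves and compares them with DeLong's test.

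**The concern.** The plan holds a pre-treatment score that it regards as prognostic for the same construct as the primary outcome, yet the primary test does not use it. If STAI-T predicts later STAI-S beyond what baseline STAI-S predicts, a pre-specified adjustment would shrink the residual variance, narrow the confidence interval and add power without recruiting anyone. In a linear model it would leave the estimated quantity unchanged.

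The exploratory model does not deliver this in full. Cutting the score at 40 discards information, and that model is not the one on which the trial will be judged.

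Only precision is at stake, not validity.

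**Working it through.** **Inputs (Section 4.4).** 75 evaluable per arm, 5-point difference, two-sided 5%, three measurements, AR(1), SD 10, correlation 0.6; 5% loss gives 79 per arm.

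**1. Reproduce the plan's figure.** The statement is: "With 75 patients per arm, 96% power would be achieved to detect a difference of 5 points in STAI-S score".
- Variance of the three-visit mean = (100/9) × [3 + 2 × (2 × 0.6 + 0.36)] = 68.0.
- SE = √(2 × 68.0/75) = 1.347.
- Power = Φ(5/1.347 − 1.96) = 96.0%, as stated (95.8% with the noncentral t).
- 75/0.95 = 78.9, so 79 per arm, as stated.

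**2. Power of the model in Section 10.3.** That model takes T1 and T2 as outcomes and T0 as a covariate. Use the mean of T1 and T2, with a 5-point effect at both visits and no effect assumed for age group.
- Variance of the mean = (100 + 100 + 2 × 60)/4 = 80.0. Power without baseline adjustment is 92.8%.
- Covariance with T0 = (60 + 36)/2 = 48, so the correlation is 48/(10 × √80) = 0.537.
- Residual variance given T0 = 80 − 48²/100 = 56.96, which is 71% of 80.
- SE = √(2 × 56.96/75) = 1.232, and power is 98.2%.

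**3. Add continuous STAI-T.** Let r be its partial correlation with the T1/T2 mean given T0 STAI-S. The documents do not give r, so it is an assumption. The residual variance becomes 56.96 × (1 − r²).

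| Assumed r | SE | Change in SE | 95% CI half-width | Power |
|---|---|---|---|---|
| none added | 1.232 | – | 2.42 | 98.2% |
| 0.1 | 1.226 | −0.5% | 2.40 | 98.3% |
| 0.2 | 1.208 | −2.0% | 2.37 | 98.5% |
| 0.3 | 1.176 | −4.6% | 2.30 | 98.9% |

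These rows ignore the cost of one degree of freedom. With 150 patients and four terms already fitted (intercept, arm, T0, age group), that cost is √(146/145) = 1.003, or about +0.3%. This is the whole effect if r = 0.

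For each visit alone at r = 0.3, T1 goes from 96.9% to 98.0% and T2 from 90.7% to 93.1%.

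**4. How plausible is each r?** Write a for the correlation of STAI-T with T0 STAI-S, and b for its correlation with the T1/T2 mean (both assumed). Then r = (b − 0.537a)/√[(1 − 0.537²)(1 − a²)].
- a = 0.7, b = 0.4: r = 0.04, and the SE falls by about 0.1%.
- a = 0.7, b = 0.5: r = 0.21, and the SE falls by about 2%.
- a = 0.7: r = 0.3 needs b = 0.56, and r = 0.4 needs b = 0.62. Both exceed the 0.537 that T0 STAI-S itself achieves.
- a = 0.5, b = 0.5: r = 0.32, so 0.3 is easier to reach if the two scales overlap less.

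**5. If the planning values are optimistic.** For the T1/T2 mean with 75 per arm, power without STAI-T and with r = 0.3 is:
- 4 points, SD 10: 90.1% to 92.5%.
- 4 points, SD 12: 77.2% to 80.9%.
- 3 points, SD 10: 68.2% to 72.3%.

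**The case against.** The case for leaving Section 10.3 alone is strong on most counts.

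- **No error.** The model adjusts for the baseline of the outcome and for the only stratification factor. Leaving out a further covariate neither biases a randomized comparison nor disturbs the type I error. This stands in full.
- **Little power to gain.** With 98.2% on the planning inputs there is almost no room. This stands; what remains is interval width and robustness to the planning values.
- **Size unknown.** The partial correlation is not in the documents and may be close to zero. This stands, and an r of 0.3 or more is demanding if the two scales overlap strongly.
- **Already handled.** The exploratory model without interaction gives a trait-adjusted arm effect. This stands in part: that estimate uses a dichotomized score and does not change the primary test.
- **Why STAI-T and not HADS-A?** Section 8.3.2 gives HADS-A a parallel role, and the trial sets out to compare the two. The documents do not rank them, so the choice is a judgement. That is a reason to fix it in advance, not a drawback of adjusting.

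A reader might also infer that large precision is being wasted, because under AR(1) baseline STAI-S leaves 64% of the T1 variance (1 − 0.6²) and 87% of the T2 variance (1 − 0.36²) unexplained. The documents do not support that reading. For the T1/T2 mean the unexplained share is 71%, and nothing shows how much of it is trait rather than situation. The 87% comes from the assumed AR(1) decay, whereas Section 10.3 will choose the correlation structure by information criteria. Nor is it an argument that baseline STAI-S is taken online, away from surgery: STAI-T is collected at the same T0 session.

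**Conclusion.** The point holds as an optional, nearly free improvement. A pre-treatment score requested from everyone, and described by the protocol as a risk marker, could be used in continuous form in the primary model and is not.

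The likely size is small: an SE change between about +0.3% (r = 0) and −4.6% (r = 0.3), and on the planning inputs a power gain of at most about 0.7 percentage points over that range. The gain in power becomes visible, at roughly 2 to 4 points for r = 0.3, only if the true effect is smaller or the SD larger than planned.

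These figures rest on the Section 4.4 values (SD 10, AR(1) with 0.6), an equal effect at T1 and T2, no assumed age effect, and an assumed r.

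It would be wrong to conclude that the primary analysis is biased, that the trial is underpowered for want of this covariate, or that STAI-T goes unused.

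**What to change.** In Section 10.3, before any outcome data are seen:

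1. Add the continuous T0 STAI-T score as a covariate in the primary mixed model, beside T0 STAI-S and age group.
2. Report the model without STAI-T as a named sensitivity analysis.
3. Keep the trait-by-arm interaction, and the versions dichotomized at the cut-offs, in the exploratory analysis.
4. State how a missing baseline STAI-T is handled; imputing the overall baseline mean is enough to keep the patient in the model.

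The cost is a short edit and one degree of freedom (about 0.3% on the SE if the score proves uninformative). No new data and no change in sample size are needed. Timing matters: the same covariate added after outcomes are known would invite the charge of selective adjustment.

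### The exploratory models in Section 10.3 use baseline STAI-T and HADS-A only as yes/no variables, although both full scores are collected; continuous terms would usually retain more information

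*Combined protocol and SAP*

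**What the plan says.** Section 10.3 first sets out the primary analysis: a repeated-measures mixed model for STAI-S at T1 and T2, adjusted for baseline STAI-S and age group. It then describes a separate analysis, which it labels exploratory, in which "STAI-T at baseline (dichotomized for anxiety status with cut-off 40 (see protocol Section 8.3.2) will be added as an explanatory variable", with and without an interaction with study arm. For the second instrument it adds: "The same will be done with HADS-A at baseline, dichotomized using cut-off 8 (Section 8.3.2".

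Section 8.3.2 shows what is available. Participants complete the full trait scale (20 to 80) and the full HADS-A (0 to 21) at baseline. The section describes 40 as a commonly used STAI threshold, and for HADS-A it says: "A subscale score above 8 denotes anxiety".

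Section 10.3 includes no model with either score as a continuous covariate. Section 10.4 analyses both instruments by ROC curves, which answers a different question from effect modification.

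**The concern.** After the split, a trait score of 41 is treated like 70 and a score of 39 like 20. If the effect of the breathing technique, or the level of STAI-S itself, changes gradually with baseline anxiety, most of that gradient lies within the two groups and is lost. The main term and the interaction are then estimated less precisely than the collected data allow. A real interaction is more likely to be missed and reported as no evidence of effect modification. The full scores are already in the database, so the loss is avoidable.

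**Working it through.** **Inputs from the documents.** Section 4.4: "With 75 patients per arm, 96% power would be achieved to detect a difference of 5 points in STAI-S score", "at the two-sided 5% significance level", "in a design with 3 measurements per patient", "having an autoregressive order 1 covariance structure", when "the standard deviation is 10 and the correlation between observations within the same patient is 0.6". Sections 8.3.2 and 10.3: the score ranges and the cuts at 40 and 8. The documents give no mean, SD or share above the cut for STAI-T or HADS-A.

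**Step 1: reproduce the plan's own figure.** The mean of three AR(1) measurements has SD 10 × √[(3 + 4×0.6 + 2×0.36)/9] = 10 × √(6.12/9) = 8.246. The standard error of the arm difference is 8.246 × √(2/75) = 1.347, and 5/1.347 = 3.71. Power is Φ(3.71 − 1.96) = 96.0% (95.8% with the t distribution), which agrees with the stated 96%. Allowing for 5% drop-out, 75/0.95 rounds up to 79 per arm, also as stated. Neither figure involves STAI-T or HADS-A.

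**Step 2: information kept after a split.** Take a standard normal score X cut at c, with a share p above the cut. The covariance of X with the indicator is φ(c), and the indicator has variance p(1−p). For a linear effect, relative efficiency is the squared correlation, φ(c)²/[p(1−p)]. With 1:1 allocation the same factor applies to the slope in each arm, and so to the interaction.

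| Share above cut (assumed) | Efficiency | Information lost |
|---|---|---|
| 50% | 0.3989²/0.25 = 0.637 | 36% |
| 35% | 0.3704²/0.2275 = 0.603 | 40% |
| 20% | 0.2800²/0.16 = 0.490 | 51% |
| 15% | 0.426 | 57% |
| 10% | 0.342 | 66% |

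The formula is symmetric, so 80% above the cut gives the same result as 20%. At 50:50, 150 patients carry the information of about 150 × 0.637 ≈ 95. At 80:20 they carry that of about 150 × 0.490 ≈ 73.

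**Step 3: simulation check of the loss.** With 150 patients and a linear arm-by-score interaction, the simulated loss for a normal score was 37%, 40% and 53% at 50%, 35% and 20% above the cut. For a right-skewed score it was 40%, 35% and 42%.

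**Step 4: what this means for interaction power.** The residual SD is that of the T1–T2 mean given T0 under the Section 4.4 assumptions: √[(64 + 87.04 + 2×38.4)/4] = √56.96 = 7.55. The interaction sizes are assumptions; the documents give none.

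- 3.2 points per SD of the score: about 70–73% power with the continuous score, against 52%, 51% and 41% when split at 50%, 35% and 20% above the cut.
- 2 points per SD (residual SD 7.5): about 35%, against 19–26%.
- 1 point per SD (residual SD 7.5): 12–13%, against about 9%.

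**Step 5: the opposite case.** Suppose the arm effect instead changes by 7 points exactly at the cut (assumed; residual SD 7.5). The dichotomised term then has 79%, 76% and 60% power at 50%, 35% and 20% above the cut, and the linear continuous term has 59%, 52% and 35%.

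**The case against.** The strongest defence has four parts.

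- **The analysis is exploratory.** Section 10.3 labels it so. No objective or hypothesis in Section 2 mentions effect modification, and the primary model uses neither dichotomised variable. This stands. A reader might infer that the trial's main result or its power is weakened; the documents give no support for that.

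- **The cuts are pre-specified, recognisable thresholds.** Section 8.3.2 says the instruments are there to identify patients at high risk of anxiety or with high anxiety, and cut-offs suit that use. This stands as a reason to report results at the thresholds. It is not a reason to leave out the rest of the score.

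- **The continuous model is not always better.** Step 5 shows that a true step at the threshold favours the split, and a curvature check uses degrees of freedom. The documents do not say which shape to expect. This stands and limits the claim.

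- **The gain may be small in practice.** An interaction of 3.2 points per SD is large beside a 5-point design effect. At 1 or 2 points per SD both versions usually miss it, so continuous modelling would not make a null interaction informative. This also stands.

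A reader might also see a contradiction between a cut-off of 8 in Section 10.3 and a score above 8 in Section 8.3.2. There is none: Section 10.3 refers to Section 8.3.2, which supplies the direction, so a HADS-A of exactly 8 is not high.

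**Conclusion.** The point holds as an optional improvement to an exploratory analysis. As planned, these models discard a material part of two scores the trial collects in full: roughly 36% at a 50:50 split and 51% at 80:20, given an approximately normal score and an approximately linear relation.

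It would be tempting to quote 36–51% as the loss in this trial. The documents do not support that, because they do not state the share above either cut. Nor is the range a bound: the loss is larger for a normal score with fewer than 20% above the cut, and was about 35–42% for the skewed scores simulated. If the effect steps at the threshold, the comparison reverses.

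**What to change.** In Section 10.3, make the main exploratory models use continuous STAI-T and, separately, continuous HADS-A, each with and without a continuous-by-arm interaction and with a check for curvature. Report the estimated arm effect with its 95% confidence interval at chosen scores, including 40 and 8. Keep the pre-specified dichotomised results as supportive or descriptive, which also covers a true step at the threshold. When editing, state which group a STAI-T of exactly 40 falls in, since neither section says so.

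The change needs SAP wording only: same data, same model family, no new collection. The costs are a few degrees of freedom for the curvature check and lower power for the linear interaction term if the effect really changes at the cut-off.
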